11.2.2. Adverse Event Reporting

Pennington Biomedical Research Center is an AAHRPP accredited institution and, above all else, is committed to ensuring and maintaining the safety of its participants. Due diligence will be applied to ensure that study subjects are not exposed to undue or untoward risk. Any significant health problems that come to our attention during the study will be referred to the participant's usual source of medical care, with her permission. We will cooperate fully with her physician by providing relevant medical records.

Adverse events will be documented during the scheduled visits, evaluated by the Medical Monitor for severity and relatedness, and reported according to the reporting policy requirements of the IRB of the Pennington Biomedical Research Center. For each sign, symptom or adverse event, the following information will be recorded:

- A brief descriptor of the adverse event
- Start and stop dates
- Intensity (mild / moderate / severe)
- Whether the AE was "serious" or not (as defined below)
- Causal association with the intervention assigned (none / doubtful / possibly / probably / very likely)
- Outcome (resolved / resolved with sequelae / improving / still present and unchanged / death)
- Action taken with respect to the intervention (none / intervention temporarily discontinued / medical therapy required / intervention permanently discontinued / other).

Unanticipated problems involving risks to participants or others include incidents only if the incident is unexpected, related or possibly related to participation in the research, and indicated that subjects or others are at a greater risk of harm than was previously known or recognized.

11.2.3. Additional Safety Monitoring

Additional safety monitoring is included in this study. Identification of the following would generate a safety alert and require specific action if noted during any study visit:

- Contraindications to moderate to high intensity physical activity during pregnancy
 - Incompetent cervix/cerclage
 - Persistent 2nd or 3rd trimester bleeding
 - Placenta previa after 26 weeks' gestation
 - Premature labor that requires hospitalization and treatment with medications to stop contractions
 - Ruptured membranes
 - Preeclampsia / gestational hypertension
 - Severe anemia defined as a hemoglobin < 8 or hematocrit < 24

****If any of these conditions are reported, study staff will notify the PI and interventionist(s) that the participant has developed a contraindication to moderate- to high-intensity physical activity in pregnancy. The physical activity component(s) of the intervention may need to be modified. The presence of any of the conditions may not

require a change in any dietary component(s) of the intervention. Participants for whom a change to intervention component(s) is indicated should not be considered withdrawn from the study.

- High blood pressure
 - If measured blood pressure is ≥ 160/110, i.e. systolic blood pressure ≥ 160 mm Hg and/or diastolic blood pressure ≥ 110 mm Hg, study staff will consult with the study MI or his designee. Staff will contact the participant's provider as recommended by the study MI.
 - o If measured blood pressure is ≥ 140/90, i.e. systolic blood pressure ≥ 140 mm Hg and/or diastolic blood pressure ≥ 90 mm Hg, study staff will instruct participants to contact their provider regarding the elevated measure to arrange appropriate follow-up. Additionally, study staff will consult with the study MI or his designee to arrange follow-up as appropriate.
 - At least one blood pressure reading must meet criteria when two readings are taken, and at least two blood pressure readings must meet criteria when three readings are taken.
- Weight loss during pregnancy after randomization All participants
 For all participants, weight safety alert values will be obtained from the weight measured at the clinic visit.
 - For women who are normal weight at enrollment, alert values will be any weight loss from enrollment weight.
 - For women who are overweight at enrollment, alert values will be weight loss of 4% or greater of enrollment weight.
 - For women who are obese at enrollment, alert values will be weight loss of 6% or greater of enrollment weight.
 - Safety alert procedures:
 - For the first weight loss alert, the research staff will notify the participant, and ask the participant to return to clinic for a study visit weight within 2 weeks. Repeat weights should be collected at the same location at which the original safety alert weight was collected. The intervention team will be notified, and if the participant is enrolled in the Healthy Beginnings program, the intervention team will discuss her energy balance activities, provide weight management counseling, and modify the intervention if appropriate.
 - If the repeat weight indicates the same or greater upon 2 week assessment, study staff will consult with the study MI or his designee. Staff will contact the participant's provider as recommended by the study MI. Additional modifications to the intervention may be indicated (i.e. decrease exercise, increase caloric intake). If the weight upon reassessment no longer meets the alert value criteria, the participant will continue current study activity.
- Weight loss during pregnancy after randomization Healthy Beginnings participants only
 For participants in the Healthy Beginnings program, weight monitoring values will also be obtained from
 the Bodytrace scale and based on either change in weight from the beginning of the intervention or a
 change in weight from week to week. It is important to note women can remain in the Institute of
 Medicine recommended weight range and not gain weight for a week or longer, even women with normal
 weight. Thus, no weight gain for short periods of time (1-4 weeks) can be acceptable.
 - For women who are normal weight at enrollment, weight monitoring values will be weekly weight loss from the first Bodytrace scale weight for two consecutive weeks.
 - For women who are overweight at enrollment, weight monitoring values will be weight loss of 4% or greater from the first Bodytrace scale weight or 4% or greater weekly weight loss.

- For women who are obese at enrollment, weight monitoring values will be weight loss of 6% or greater from the first Bodytrace scale weight or 6% or greater weekly weight loss.
- Monitoring and safety alert procedures:
 - The first Bodytrace scale weight monitoring value will trigger close monitoring by the intervention staff. The intervention team will discuss her energy balance activities, provide weight management counseling, and modify the intervention if appropriate including strategies to increase food intake, decrease weighing frequency, and other toolbox options.
 - If a second Bodytrace scale weight monitoring value occurs within 2 consecutive weeks and after intervention monitoring and adjustments, a safety alert will be documented. Staff will contact the participant's provider as recommended by the study MI. Additional modifications to the intervention may be indicated (i.e. decrease exercise, increase caloric intake). If the weight upon reassessment no longer meets the alert value criteria, the participant will continue current study activity.

11.2.4. Stopping rules

This study does not involve major risk for participating. Nevertheless, we will follow the 2009 Recommendations of the American College of Obstetrician and Gynecologist, Committee on Obstetric Practice^[47] to determine if temporary and permanent discontinuation of the intervention of a participant is required due to the safety concerns. Modifications to the intervention or complete but temporary discontinuation will be determined on a case-by-case basis.

- Criteria for **Temporary Discontinuation** of the Intervention
 - o Severe anemia
 - Intrauterine growth restriction in current pregnancy
 - o Other complications identified by the Medical Monitor or the participant's provider
- Criteria for Permanent Discontinuation of the Intervention
 - Premature labor in current pregnancy
 - Ruptured membranes
 - o Preeclampsia
 - o Persistent second or third trimester bleeding
 - o Other complications identified by the Medical Monitor or the participant's provider

11.3. Confidentiality

All personnel involved in the design and conduct of this research project will receive the required education on the protection of human subjects prior to the start of the study. An individual record will be kept for each subject. This record will contain identifying data, demographic information, medical history, and results of physical examination and medical tests. Study samples and data sheets will be coded with an identification number for each subject. All data will be treated with confidentiality and the subjects' names and identities will not be disclosed in any published reports. Clinic records are maintained in locked file cabinets in a locked file room. Access to these areas is limited to the clinical support staff, director of the WIC facilities, and the PI. Electronic data storage is similarly restricted with only authorized persons having access to databases containing confidential clinical records, i.e. those containing name or other potential identifying information. The coded participant list identifying participants by name will be stored separately from the number coded records/questionnaires/data. Study results will be reported as group data and/or by participant identification number only. Study results may be presented in publications or at meetings/conferences, however participant identity will not be disclosed. A participant may request their personal health information or their personal study data/results at any time during the study and will be given copies.

11.4. Informed Consent

Informed consenting is only permitted by the clinical research specialist or project manager or other qualified person (determined by the PI) who has completed CITI training in human subjects' research and has completed study familiarization training by the Principal Investigator. Confidentiality is assured at all times as well as the right not to participate or to withdraw at any time without prejudice. Interested participants will sign and date the informed consent forms and will be given a copy to retain for their records. Names and telephone numbers of contact persons on the investigative team, including a 24h number are given to the participant for use if future questions arise at any point throughout participation in the study.

11.5. HIPAA Compliance

The Pennington Biomedical Research Center complies with the federal 1996 Health Insurance Portability and Accountability Act (HIPAA). Specifically, PBRC protects the privacy and confidentiality of medical records and information contained in medical records of persons who are subjects of research projects, including all protected health information (PHI) as defined by the HIPAA Privacy Regulations. PHI of research subjects and the use or disclosure of such information is governed by PBRC research policies, as well as Common Rule, FDA regulations, and other applicable laws.

PBRC and the PI protect the privacy of research subjects and their PHI collected during a research project. PBRC will not use or disclose existing PHI or PHI created during a research project, unless:

- The subject signs both (a) a HIPAA Authorization for use and disclosure of PHI using an approved Authorization Form or other form containing all the elements of legally effective HIPAA authorization and (b) the informed consent to participate in research form approved by the IRB, or
- The IRB grants a waiver to the requirement of obtaining a signed HIPAA Authorization Form, or
- The IRB-approved protocol uses properly de-identified PHI
- The IRB-approved protocol uses the limited data set and the PI signs a limited data use agreement with the entity that maintains the designated record set.

12. DATA MANAGEMENT

12.1. Data Collection

Pennington Biomedical uses a study-specific data management system in RedCap (81) which allows for real-time, web-based data entry for community-based studies. All collected data are entered into the central RedCap (81) database that undergoes continuous quality assurance by the PBRC Research Computing Core. All data are stored on a server backed-up daily and the Research Computing Core oversees data management.

12.2. Sample Size Consideration

To observe a 14% increase in the incidence rate of GWG (**Hypothesis A**), and accounting for 15% attrition, a total of 432 participants with 1:1 allocation between the two groups (SmartMoms[®] and Usual Care) and equal stratification across the three BMI categories (n=144) is required to detect a significant difference. The sample size estimates assume β =0.8 and α =0.05 to detect the specified increases in the incidence rate of appropriate GWG. The incidence rates of appropriate GWG for the Usual Care group were derived from women receiving WIC benefits in the 2013 Louisiana Pregnancy Risk Assessment Monitoring System data (95). The estimated effect size is based on our pilot trial data where the incidence rate of appropriate GWG for Usual Care versus 43.8% in SmartMoms[®]; and for obese women 0% for Usual Care and 42.9% in SmartMoms[®]. However since the pilot trial was not in an exclusive under-served population, we conservatively estimate that the SmartMoms[®] intervention will increase the incidence rate by a minimum of 14% across each BMI category.

This study is also powered to detect BMI group changes in incidence rates. Assuming an overall average change in incidence rate of 14%, 125 participants in each BMI group (accounting for 15% attrition) is sufficient to detect an incidence rate that is at least 20% different between BMI groups.

In addition, we will also investigate the rate of GWG per week (**Hypothesis B**). Per the 2009 IOM guidelines, each BMI category is allocated a different rate of GWG per week (79). We will investigate the deviation between the observed rates of GWG and rates deemed appropriate by the 2009 IOM. Our pilot data from the 'Expecting Success' study showed that both overweight and obese women in the SmartMoms[®] gained an additional 0.06 kg/week above the recommended amount, which was approximately 3 times higher in the Usual Care groups (0.21 and 0.16 kg/week for overweight and obese women respectively). With our planned sample size of 432 participants, we have more than 80% power to detect change a change as small as 0.12 kg/week between SmartMoms[®] and Usual Care and within each BMI category and over 99% power to show overall differences in rates of weekly GWG.

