2.2. Endpoints

Primary endpoint:

• Incidence of appropriate weight gain in pregnancy as defined by the 2009 IOM Guidelines [2].

Secondary endpoints:

- Rate of GWG per week
- Maternal diet (24h recall)
- Physical activity (Accelerometry, Pregnancy Physical Activity Questionnaire)
- Quality of life and stress (Depression Anxiety Stress Scales-21, Quality of Life Inventory, Household Chaos Questionnaire)
- Maternal and infant birth outcomes
- Infant feeding style (Infant Feeding Style questionnaire and Breastfeeding Questionnaire)
- WIC food voucher redemption rate
- Postpartum weight retention (measured 1, 6 and 12 months after delivery)

Exploratory endpoints: This study is also powered for a comparison of GWG between BMI categories. As an exploratory aim we will test whether maternal body mass index (BMI) is a moderator of intervention effects on GWG (relative to Usual Care).

Planned post-hoc analyses include testing moderators of intervention effects on GWG in BMI categories, race/ethnicity groups and in the SmartMoms[®] group only, intervention adherence.

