2.3 Sample Size and Study Power

Study hypotheses will be assessed using appropriate statistical tests, input variables and endpoints, and therefore, power calculations and sample size estimates are presented for the study aims. Estimates of the study power are derived from our preliminary data and from existing literature. The 1:1 randomization scheme within each BMI stratum is applied to ensure that the study is also sufficiently powered to compare intervention effectiveness within BMI groups which is important for the program announcement (PA-18-135).

The sample size estimates assume β =0.8 and α =0.05 to detect the specified differences between incidence rates of appropriate GWG. All sample sizes are inflated to account for 15% attrition. Intent-to-treat (ITT) analyses will be used. Participants are required to have at least one follow-up clinic weight to compute GWG (incidence rate, study observed, per week, and deviation). We plan to enrol at least 330 participants, with relative balance within each BMI stratum. We have sufficient power for our primary comparisons of GWG as well as comparisons within BMI groups. Due to the Covid-19 pandemic impacting trial procedures and enrolment, the goal of this study is to enrol at least 330 participants. That is, the study will continue to enrol individuals until either the end of the enrolment period (December 2023, with participants having to be certified to receive WIC benefits by October 31, 2023, to be eligible) or until all three BMI categories have 110 enrolled participants. Enrolment in any given BMI category will continue past 110 if the other BMI categories have yet to meet the enrolment goal.

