4.3 Analyses of Study Aims

Hypothesis 1: The incidence of appropriate study observed GWG per week according to the 2009 Institute of Medicine guidelines¹ will be higher in the SmartMoms® group as compared to the Usual Care group.

The categorical outcome of study-observed GWG per week attainment will be analyzed using a general linear model with a fixed effect for group (SmartMoms®, Usual Care) with a binary distribution and a log odd link function modeling the incidence rates. Covariates will include BMI category (normal weight, overweight, obesity) at randomization, parity (nulliparous, non-nulliparous), and gestational age at randomization. Results will be reported as adjusted odds ratios (OR) and/or relative risks (RR) as appropriate. The analysis will also be conducted and reported within each BMI category.

Hypothesis 2: Study observed GWG seen in the SmartMoms® group will be less as compared to the Usual Care group. This will be assessed using the following three measures: study observed GWG, weekly GWG, and deviation from the 2009 Institute of Medicine guidelines.¹

The continuous outcome of study observed GWG will be analyzed using a linear mixed-effects model including fixed effects for time (early pregnancy, late pregnancy), group, and the interaction thereof, with participant as a random effect to account for within-participant repeated measures as well as BMI category (normal weight, overweight, obesity) at randomization, parity (nulliparous, non-nulliparous), and gestational age at randomization as covariates. The continuous outcomes related to study observed GWG per week assessed only during late pregnancy (i.e., weekly GWG and deviation from the 2009 Institute of Medicine guidelines) will be analyzed analogously using a linear model with a fixed effect for group and the same covariates. The analysis will also be conducted and reported within each BMI category.

Exploratory: The incidence of adverse perinatal outcomes will be less in the SmartMoms® group as compared to the Usual Care group.

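### The protocol's 20-point BMI power figure fits a comparison of incidence between BMI groups, not the moderator aim it is placed beside; that aim has roughly 30–41% power and no specified group-by-BMI model

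*Protocol*

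**What the plan says.** Protocol 2.2, under the exploratory endpoints, says: "This study is also powered for a comparison of GWG between BMI categories". The next sentence gives the aim: "As an exploratory aim we will test whether maternal body mass index (BMI) is a moderator of intervention effects on GWG". BMI category appears again there among the planned post-hoc moderator analyses.

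Protocol 12.2 gives the figure. It opens with "Assuming an overall average change in incidence rate of 14" per cent and concludes that 125 per BMI group, after attrition, are "sufficient to detect an incidence rate that is at least 20% different between BMI groups".

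Protocol 12.3 plans contingency tables of incidence against treatment or BMI category with chi-squared tests, then two sets of models. One set has treatment and BMI category only; the other adds covariates selected by LARS. Pairwise comparisons of category variables are to be corrected for multiplicity when necessary.

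The SAP lowers the target to at least 330. It does not repeat the 20-point statement; section 2.3.1 gives 26 points between arms within a stratum instead. BMI category enters the SAP 4.3 models as a covariate, and for subgroups: "The analysis will also be conducted and reported within each BMI category". The amendment notes record that the mediation and moderator section was removed because those analyses are exploratory.

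**The concern.** In Protocol 2.2 the power statement and the moderator aim are consecutive sentences. In 12.2 the 20 points are introduced by an average change of 14 points, which is the SmartMoms versus Usual Care effect from the paragraph before. A reader can easily conclude that the trial has 80% power to show that the intervention works differently across BMI groups. Moderation is a difference between two treatment effects, and its variance is the sum over four cells, so a sample that suffices for a comparison of BMI groups falls well short.

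The second part concerns the analysis. If the only BMI analyses are three separate ones, the moderator aim has no test. A mix of significant and non-significant strata may then be taken as moderation, which separate tests cannot show.

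**Working it through.** **Inputs.** The protocol states "The sample size estimates assume β =0.8 and α =0.05"; I read this as 80% power and assume a two-sided test, since sidedness is not given. Usual Care rates from SAP Table 1 are 36.9% (normal weight), 23.9% (overweight) and 25.2% (obesity), 28.7% overall. The average effect is 14 points. The original size is "a total of 432 participants with 1:1 allocation between the two groups", in three equal BMI categories. On attrition the SAP says: "All sample sizes are inflated to account for 15% attrition". Evaluable women per arm-by-BMI cell are therefore 432/6 × 0.85 = 61.2, and 330/6 × 0.85 = 46.75.

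**Check of the method.** The pooled two-proportion formula for 28.7% against 42.7% needs 183 per arm, 366 in total, and 366/0.85 = 431. The plan says 432.

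**1. The plan's 20-point figure.** Read it as incidence in two BMI groups, arms pooled. The averages of Usual Care and SmartMoms rates are 43.9%, 30.9% and 32.2%. Power = Φ{(d − z√(2p̄(1−p̄)/n)) / √([p₁(1−p₁)+p₂(1−p₂)]/n)}.

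For 30.9% against 50.9% with n = 125:
- p̄ = 0.409; null SE = √(0.4834/125) = 0.0622; alternative SE = √(0.4634/125) = 0.0609.
- α = 0.05: (0.20 − 1.96 × 0.0622)/0.0609 = 1.28, power 90%.
- α = 0.05/3: (0.20 − 2.394 × 0.0622)/0.0609 = 0.84, power 80%.

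Over the three base rates the results are 89–90%, and 79–80% with Bonferroni. Other readings of the 20 points do not reach 80%: between arms within one BMI group (62.5 per arm) gives 61–66%, and between BMI groups in the SmartMoms arm alone 61–71%.

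**2. The moderator aim.** Take effects of 24 and 4 points, which differ by 20 and average 14. SE = √(Σp(1−p)/n) over four cells; power = Φ(0.20/SE − 1.96).

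For normal weight (36.9% to 60.9%) against overweight (23.9% to 27.9%), Σp(1−p) = 0.2328 + 0.2381 + 0.1819 + 0.2012 = 0.854:
- n = 61.2: SE = 0.118; Φ(1.69 − 1.96) = 39%.
- n = 46.75: SE = 0.135; Φ(1.48 − 1.96) = 32%.

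Ranges over all BMI pairs, in both directions:

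| | N=432 | N=330 |
|---|---|---|
| Risk difference, 15% attrition | 37–41% | 30–33% |
| Risk difference, no attrition | 43–47% | 34–37% |
| Log-odds, 15% attrition | 28–39% | 23–31% |

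The log-odds row uses the same cells. For the worked pair the difference in log odds ratios is 0.771 with SE √(18.96/61.2) = 0.557, so Φ(1.38 − 1.96) = 28%.

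**3. What the sample can detect.** Setting the effects at 14 ± D/2 points and solving D/SE = 1.96 + 0.84 gives D of about 32–34 points at N=432 and 36–39 at N=330. For 80% power at 20 points, n per cell = Σp(1−p) × (2.80/0.20)². With a sum of 0.88, inside the 0.82–0.91 range over pairs, this is about 173 per cell, 1,038 evaluable and about 1,220 randomized.

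**4. Separate analyses.** Suppose the true effect is 20 points in every stratum, so there is no moderation. At 46.75 per arm, power within a stratum is 49%, 53% and 53%. All three are significant with probability 0.49 × 0.53 × 0.53 = 0.14, and none with 0.51 × 0.47 × 0.47 = 0.11. A mixed pattern then arises in about 75% of trials.

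**The case against.** The strongest reply is that the sentence in 12.2 is correct as written. Its object is an incidence rate, not a treatment effect, and on that reading the arithmetic reproduces. With three corrected pairwise comparisons the need is 126–129 per group, close to the stated 125. Protocol 12.3 plans this very comparison, so it is not an idle reading. In 2.2 the power statement and the moderator aim are separate sentences, and the aim is labelled exploratory. The SAP drops the 20-point statement, explains the removal of its moderator section, and in section 3 warns that secondary and exploratory results are not definitive.

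Most of this stands. A reader might infer that the protocol claims 80% power for moderation and has miscalculated, or that the 330 target breaks a promise in the SAP. The documents support neither: no power is stated for an interaction, and the SAP makes no between-BMI claim. It is also conjecture that the authors will contrast subgroup p-values.

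Two things remain. The phrases about BMI group changes and an average change of 14 points do point towards treatment effects, so the wording misleads. And calling moderation exploratory explains why it left the primary results, but does not supply a model for an aim that the protocol retains.

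**Conclusion.** The point holds as a matter of clarity and of a missing analysis, not as an arithmetic error. The 20-point figure is sound for incidence between BMI groups with arms pooled. It gives no support to the moderator aim, where power for the same 20 points is about 37–41% at N=432 and 30–33% at N=330, and lower on the log-odds scale of the planned model. No choice of scale or attrition examined brings it near 80%.

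These figures concern the binary endpoint and rest on a two-sided 5% test, 15% attrition unless stated, SAP Table 1 control rates, equal cells and one uncorrected pairwise contrast. They ignore site effects and covariates. The N=330 figures describe what the current sample can deliver; they do not contradict any sentence in the SAP.

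Neither document names a group-by-BMI term, so as written the trial would report effects within BMI groups without testing whether they differ.

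**What to change.** In Protocol 2.2 and 12.2, state that the 20-point figure refers to incidence of appropriate gain between BMI groups with arms pooled, and whether it allows for three corrected pairwise comparisons. Add that the moderator test is exploratory and has low power, citing the range on the scale of the model to be used.

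In SAP 4.3, add one exploratory model with group, BMI category and their interaction plus the existing covariates. Report the interaction with its confidence interval, and take the within-BMI estimates from this model instead of from three separate fits.

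The cost is a few sentences, one extra model and a power statement that looks less favourable. No sample size or primary analysis changes.
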